5.1 Inclusion criteria

Patients eligible for inclusion in this study have to meet **all** of the following criteria:

1. Histologically documented diagnosis of squamous cell carcinoma of the head/neck including nasopharyngeal carcinomas (lymphoepithelioma histology is ok if criteria 2 is met).
 - Patients must have progressed on prior platinum based therapy (or have become intolerant) prior to enrollment on this study.
 - Prior anti-PD-1 or other immunotherapy is acceptable
2. FGFR genetic alterations (specifically FGFR1-3 mutation, amplification, or translocation) via DNA or RNA based assay. Prescreening has to be completed prior to enrollment on this study. Commercial or local testing is typically expected, but samples can also be sent to the Univ. of Chicago for testing (see 4.1.1).

The following genetic aberrations will be screened for (please also see 4.1.1):

- **FGFR1 amplification, FGFR1 somatic mutations, FGFR1 translocations.**
- **FGFR2 somatic mutations, FGFR2 translocations, FGFR2 amplification.**
- **FGFR3 somatic mutations, FGFR3 translocations, FGFR3 amplification.**

Other genetic FGF/FGFR pathway aberrations may be acceptable should such genetic changes be observed to emerge and require approval per the Lead Investigator for enrollment (e.g. FGF amplification).

Should one genetic aberration be overrepresented in one or both of the arms the Lead Investigator ([name]) may decide to restrict enrollment of such patients. A notification/memo will be sent out to all investigators should such a restriction on enrollment be implemented (see inclusion criteria). For example, if more than 5 pts with FGFR1 amplification are enrolled further enrollment of FGFR1 amplified patients will be put on hold, or if FGFR translocations are under-represented enrollment may be focused on this aberration.

3. Consent to undergo a fresh biopsy in case of benefit from therapy and subsequent progression (see 7.2.5)
4. ECOG performance status ≤ 1
5. Patients must provide written informed consent prior to any screening procedures.
6. Age 18 years or older.
7. Willing and able to comply with scheduled visits, treatment plan and laboratory tests
8. Patient is able to swallow and retain oral medication, unless approval per the manufacturer of other administration routes/methods is provided.
9. Recovery from adverse events of previous systemic anti-cancer therapies to baseline or grade 1, except for:
 - Alopecia

- Stable neuropathy of \leq grade 2 due to prior cancer therapy
10. HPV status in Oropharyngeal Carcinomas. While HPV status (e.g. via p16) does not have to be known prior to consenting, the HPV status (e.g. using p16 IHC) needs to be established prior to start of therapy.
 11. Presence of measurable disease by RECIST 1.1
 12. Availability of tumor tissue (e.g. FFPE) for genomic profile (typically 12 unstained FFPE 5-10 micron slides, minimum of 10).

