4.1.1 FGFR aberration (pre-screening)

In order for patient to be eligible one of the following genetic aberrations need to be present in the tumor:

- FGFR1 amplification, FGFR1 somatic mutations, FGFR1 translocations.
- FGFR2 somatic mutations, FGFR2 translocations, FGFR2 amplification.
- FGFR3 somatic mutations, FGFR3 translocations, FGFR3 amplification.

NB: In order to allow a representative sampling of genetic aberrations each type of genetic aberration should be represented and enrollment for other genetic aberrations can be limited (see inclusion criteria). Such adjustments can be made by the Lead Investigator via a memo.

A number of next generation sequencing based tests are acceptable including Foundation One based testing, academic center CLIA laboratory based testing (e.g. DFCI Profile, University of Chicago large and small mutation and/or translocation panels, others). Additional commercial tests, and tests using other methodologies in a CLIA laboratory are potentially acceptable, but should be confirmed by the Lead Investigator prior to use ([name], [contact], [contact])

Testing is not part of this study, but the University of Chicago does offer limited testing for outside centers and centralized genomic profiling/prescreening can be offered through the U Chicago molecular pathologic laboratory. Please contact [name] if requesting Univ. of Chicago molecular analysis/testing.

Each cycle is 4 weeks. CT scans will be obtained every 2 cycles. This study will enroll 15 HPV (+) and 15 HPV (-) patients with HNSCC and FGFR alterations.

Primary objective will be objective response rate (ORR; complete or partial response) of BGI398 (infigratinib) in FGFR altered HPV (-) and HPV (+) SCCHN (Simon Two Stage Design). As genomic profiling will be used as a prescreening tool to identify FGFR altered tumors, an exploratory objective will be to assess efficacy of BGI398 (infigratinib) in relation to specific genetic aberrations in HPV (+) and HPV (-) FGFR altered HNSCC (i.e. FGFR3-TACC3 translocation, FGFR1 high copy number/amplification, FGFR2 mutation, FGFR3 mutation). Please refer to statistical considerations, methods, and data analysis in Section 11.

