4.7 Rationale for the study design

Based on the TCGA and our University of Chicago HNC cohort:

- FGFR2-3 mutations are estimated to occur in 5-8% of HPV (-) HNC and 10-15% of HPV (+) HNC.
- FGFR1 amplification is estimated to occur in 7-10% of HPV (-) HNC.
- FGFR3-TACC3 translocation is estimated to occur in 3-5% of either HPV (+) or HPV (-) head and neck cancers (in TCGA two TACC3-FGFR3 translocations occurred in HPV (+) HNC).
- Other translocations of FGFR genes as well as amplification of FGFR2/3 have been described to be oncogenic in other cancer types but based on absence in the TCGA HNC and Chicago HNC genomics cohort (CHGC) datasets to be rare in HNC.

The primary endpoint will be: **objective response rate** (ORR; complete or partial response).

With a **Simon Two Stage Design**, a preset **alpha level of 0.1** and **power of 80%**, we determined the minimum sample size required to detect the hypothesized response rate of 21% for BGJ398 (infigratinib): A sample of 20 FGFR altered patients will be large enough to detect a response rate of $\geq 21\%$ for BGJ398 (infigratinib) compared to a null response rate of 5% (Williamson et al. 2010) with 80% power and one-sided type I error rate of 0.10.

An interim analysis for futility will be conducted after 11 evaluable patients have been enrolled without interruption of enrollment. If 0/11 responses are seen, the study will be stopped prematurely for futility.

If at least one response is seen, an additional 9 patients will be enrolled. The results will be deemed negative (i.e., the 21% alternative will be rejected) if ≤ 2 responses are seen in 20 patients.

5 Population

Study population must meet both criteria below.

- A. Patients with recurrent/metastatic head and neck squamous cell carcinoma (HNSCC) not amenable to curative intent therapy (palliative treatment intent).
- B. Must harbor an FGFR genetic alterations (FGFR1-3 translocated, mutated, or amplified squamous cell carcinoma of the head and neck).

Enrollment target: N=20 patients. We estimate to have at least 3-5 patients with repeat tumor biopsies (mandatory for responders who subsequently demonstrate disease progression). All patients must have tumor material available for biomarker evaluation or confirmed FGFR1-3 translocated, mutated, or amplified squamous cell carcinoma of the head and neck.

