9.2 Registration Process

When a potential patient has been identified, notify the CRA via phone or email to ensure a reservation on the study ([contact] or [contact]). Reservations for potential subjects will only be held for subjects who have signed consent for that particular study.

When registering a subject, the following must occur:

- Confirm that the institution has a current IRB approval letter for the correct version of protocol/consent and has an annual update on file, if appropriate.
- Submit all required materials (Eligibility Checklist, Source documentation, & signed consent form) to confirm eligibility and required pre-study procedures to the CRA a minimum of 48 hours prior to the subject's scheduled therapy start date.
- Source documentation includes copies of all original documents that support each inclusion/exclusion criteria. The eligibility checklist does not serve as source documentation but rather as a checklist that original source documentation exists for each criterion.
- Communicate with the above CRA to ensure all necessary supporting source documents are received and the potential subject is eligible to start treatment on schedule. If there are questions about eligibility, the CRA will discuss it with the PI. PI may clarify, but not overturn, eligibility criteria.
- Affiliate sites must confirm registration of subjects by obtaining a subject study ID number from the CRA via phone, fax or email.
- If a subject does not start on the scheduled day 1 treatment date, promptly inform the CRA as the delay in start may deem the subject ineligible and/or require further or repeat testing to ensure eligibility.
- The date the patient is randomized if randomization is involved or receives treatment for the first time will be considered the patient's "OnStudy Date." The patient's subject ID will be assigned and a confirmation of registration will be issued by the CRA on this date. Subjects that sign consent and do not go "OnStudy" will be recorded in the database with the date they signed consent and the reason for not going "OnStudy" (e.g., Ineligible, Screen Failure or Withdrawn Consent).

10 Safety monitoring and reporting**10.1 Adverse Events****10.1.1 Definitions and reporting**

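### Eligibility requires an FGFR1-3 alteration, yet an exception admits other FGF/FGFR pathway changes, and nothing keeps those patients out of the 11 and the 20 that decide the trial

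*Combined protocol and SAP*

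**What the plan says.** Three places set a strict molecular requirement.

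- Section 5 (Population) opens with "Study population must meet both criteria below". Criterion B then reads "Must harbor an FGFR genetic alterations (FGFR1-3 translocated, mutated, or amplified squamous cell carcinoma of the head and neck".
- Section 4.1.1 says "In order for patient to be eligible one of the following genetic aberrations need to be present in the tumor". The list that follows holds only FGFR1, FGFR2 and FGFR3 changes, and that section gives no exception.
- Inclusion criterion 2 in Section 5.1 begins "FGFR genetic alterations (specifically FGFR1-3 mutation, amplification, or translocation) via DNA or RNA based assay".

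Later in the same criterion, and again in Section 4.1.2 (Methods of FGFR screening), the protocol adds "Other genetic FGF/FGFR pathway aberrations may be acceptable should such genetic changes be observed to emerge". These "require approval per the Lead Investigator for enrollment (e.g. FGF amplification").

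The primary objective in Section 3.1 concerns FGFR altered HNSCC, without the numerals 1-3. Section 7.3.1 defines evaluability for response by measurable disease at baseline, any study drug and at least one later scan; alteration type plays no part. Section 11.1 sizes the trial on 20 patients positive for an FGFR alteration. It stops for futility at 0 responses in 11 and calls the result negative at 2 or fewer in 20.

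**The concern.** FGF is the ligand and FGFR the receptor, as Section 1.2.1 sets out. A patient whose only change is FGF amplification therefore fails criterion B and is not FGFR altered in the sense of the primary objective. An FGFR4 change would fit the objective's wording but still fail criterion B. Both could enter under the exception.

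Once enrolled, treated and rescanned, such a patient meets the evaluability definition, and no text removes the patient from the decision counts. There is no cap, separate cohort or sensitivity analysis. The suggested subgroup list in Section 11.1 has no group for ligand changes; its residual group covers rare receptor changes.

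Two things are at stake. The first is whom the primary ORR describes. The second is the decision itself: the line falls between 2 and 3 responses, so one patient's inclusion can settle it. The trial is open label, so if the rule is left open, whether to count such a patient could be decided after the response is known, in either direction.

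**Working it through.** **Inputs from Sections 4.7 and 11.1.** Null rate 5%; alternative 21%; one-sided alpha 0.10; power 80%; first stage of 11, stop at 0 responses; 9 more patients; positive at 3 or more of 20.

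**Assumptions, not in the documents.** The number *k* of the 20 who lack an FGFR1-3 alteration, and their response rate *q*. The main illustration takes *q* = 5%, the protocol's own null rate, with *q* = 0% as a harsher case.

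**Step 1: reproduce the stated design.** With X1 ~ Bin(11, p) and X2 ~ Bin(9, p),

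P(positive) = P(X1=1)·P(X2≥2) + P(X1=2)·P(X2≥1) + P(X1≥3).

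- At p = 0.21: 0.2187 × 0.5934 + 0.2907 × 0.8801 + 0.4158 = 0.1298 + 0.2559 + 0.4158, giving 0.801 (0.8014 before rounding of terms).
- At p = 0.05: 0.3293 × 0.0712 + 0.0867 × 0.3698 + 0.0152 = 0.0235 + 0.0320 + 0.0152 = 0.0707.

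A minimax search at 5% versus 21% returns the same design: 0/11, then 2/20. The stated N, alpha ceiling and power are correct for 21%. (Section 11.1 also mentions 20%; power there is 77.1%. That is a separate matter, and 21% is used here.)

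**Step 2: replace *k* of the 20.** Let *j* of the *k* patients fall in the first 11. With random order, *j* is hypergeometric (20 patients, *k* of this type, 11 drawn). For each *j*, the first-stage count is the sum of *j* responses at rate *q* and 11 − *j* at 21%; the second-stage count is the sum of *k* − *j* at rate *q* and 9 − *k* + *j* at 21%. The same rule is applied and the results are averaged over *j*.

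Example with *k* = 1 and *q* = 5%: the patient is in stage 2 with probability 9/20 = 0.45 (power 0.7831) or in stage 1 with probability 11/20 = 0.55 (power 0.7751). The average is 0.45 × 0.7831 + 0.55 × 0.7751 = 0.779.

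| *k* of 20 | Power, *q* = 5% | Power, *q* = 0% |
|---|---|---|
| 0 | 80.1% | 80.1% |
| 1 | 77.9% | 77.2% |
| 2 | 75.4% | 73.8% |
| 3 | 72.7% | 70.1% |
| 5 | 66.6% | 61.4% |

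**Step 3: type I error.** If FGFR1-3 patients respond at 5% and exception patients also respond at 5%, the false-positive probability stays at 0.0707 for every *k*. If exception patients respond less often, it is lower. It is therefore not inflated for *q* ≤ 5%.

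**Step 4: is a lower *q* plausible?** The prevalence figures in Section 4.7 concern FGFR1-3. For an FGFR4 change, Section 1.2.1.1 gives an IC50 of 168 nM against 3 to 7 nM for FGFR1-3, that is 168/7 = 24 to 168/3 = 56 times weaker inhibition. For ligand changes the documents give no response rate, so *q* remains an assumption.

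**The case against.** The strongest reply is that a general rule followed by a written, gated exception is ordinary drafting. The exception is conditional on such changes emerging, needs Lead Investigator approval, and may never be used. In a proof-of-concept trial of a pathway inhibitor, admitting a rare pathway-positive patient is a legitimate choice. Section 2 also mentions autocrine FGFR signalling loops in head and neck cancer cell lines, so benefit in ligand-driven tumours cannot be ruled out. Response by alteration is already planned, the grouping may be adapted, and alteration is known before enrolment, so ORR in FGFR1-3 patients could be recomputed. The sample-size text can even be read as leaving ligand-only patients out of the 20.

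Much of this stands. The power losses are not forecasts, the case of 5 in 20 is extreme for a contingency, and an ORR that includes one such patient is not uninterpretable. What the reply does not answer is which count decides the trial. Section 4.1.1 and criterion B carry no exception, and Sections 7.3.1 and 11.1 do not say how these patients are handled. That they would count follows from silence, which is itself the defect.

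Two stronger readings are tempting and should not be drawn:

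- A reader might infer that the exception breaches Section 9.2, which says "PI may clarify, but not overturn, eligibility criteria". It does not: the exception is part of criterion 2, so approving a patient under it applies a criterion.
- A reader might infer that the primary objective itself requires an FGFR1-3 alteration. It says only FGFR altered; the restriction to 1-3 comes from Sections 4.1, 4.1.1, 5 and 5.1.

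**Conclusion.** The point holds as an inconsistency between the eligibility sections, together with a gap in the primary analysis. The population is defined by FGFR1-3 alterations, the exception admits patients outside it, and the plan does not say whether they enter the counts.

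The stated design is not wrong: N, alpha and power reproduce at 21%. The effect on power is conditional. It is nil if no such patient enrols. It is about 2 points for one patient and about 13 for five if they respond at 5%, or about 3 and 19 points if none respond. Those figures rest on an assumed number of patients, an assumed response rate, random order of entry and 21% in everyone else. The matter deserves correction because it is cheap to settle beforehand and awkward to settle once responses are known.

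**What to change.** State in Sections 5.1 and 11.1 that patients enrolled under the exception, without an FGFR1-3 alteration, do not count toward the first 11, the 20 or the primary ORR, and that their outcomes are listed separately. The rule uses a baseline feature known before enrolment, so it introduces no selection on outcome.

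Alternatively, delete the exception in both Section 4.1.2 and Section 5.1, so that they agree with Section 4.1.1 and criterion B. Widening criterion B and the objective to pathway alterations would also reconcile the text, but it would change the question and would need its own justification for 21%.

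The cost is one sentence in each section. Any exception patient would no longer fill a primary slot, so accrual may take slightly longer; if none enrols, there is no cost. The design parameters do not change.

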5.2 Exclusion criteria

Patients eligible for this study must not meet **any** of the following criteria:

1. History of another primary malignancy except adequately treated in situ carcinoma of the cervix or non-melanoma carcinoma of the skin or any other curatively treated malignancy that has not been treated in the prior 3 months or expected to require treatment for recurrence during the course of the study.
2. Patients with metastatic CNS tumors are allowed provided that they are clinically stable for a period of 30 days prior to study entry and there is not a requirement for steroid (other than close to physiologic doses) or anti-convulsant therapy. Patients with leptomeningeal involvement are excluded.
3. Patients who received a prior selective FGFR inhibitor in the recurrent/metastatic disease setting. Prior use of a multikinase inhibitor that includes anti-FGFR activity is acceptable after review by the Lead Investigator ([name]).
4. History and/or current evidence of tissue calcification including, but not limited to, the soft tissue, kidneys, intestine, myocardium and lung with the exception of calcified lymph nodes and asymptomatic coronary calcification
5. Current evidence of corneal or retinal disorder/keratopathy including, but not limited to , bullous/band keratopathy, corneal abrasion, inflammation/ulceration, keratoconjunctivitis, confirmed by ophthalmologic examination
6. Impairment of gastrointestinal (GI) function or GI disease that may significantly alter the absorption of oral BGJ398 (infigratinib) (e.g., ulcerative diseases, uncontrolled nausea, vomiting, diarrhea, malabsorption syndrome, small bowel resection)
7. History and/or current evidence of endocrine alterations of calcium/phosphate homeostasis, e.g., parathyroid disorders, history of parathyroidectomy, tumor lysis, tumoral calcinosis, etc unless the lead investigator obtains approval from Novartis.
8. Treatment with any of the following anti-cancer therapies prior to the first dose of BGJ398 (infigratinib) within the stated timeframes
 - Cyclical chemotherapy (intravenous) within a period of 2 weeks unless there are ongoing side effects $>$ Grade 2.
 - Biological therapy (including small molecules, and/or) within a period of time that is ≤ 2 weeks prior to starting study drug unless there are ongoing side effects $>$ Grade 2.
 - Any other investigational agents within a period ≤ 2 weeks prior to starting study drug unless there are ongoing side effects $>$ Grade 2.
 - Wide field radiotherapy (including radioisotopes) ≤ 2 weeks prior to starting study drug unless there are ongoing side effects $>$ Grade 2.

9. Patients who are currently receiving treatment with agents that are known strong inducers or inhibitors of CYP3A4 are prohibited.
10. Enzyme inducing anti-epileptic drugs.
11. Consumption of grapefruit, grapefruit juice, pomegranates, star fruits, Seville oranges or products within 7 days prior to first dose.
12. Use of medications that are known to prolong the QT interval and/or are associated with a risk of Torsades de Pointes 7 days prior to first dose.
13. Use of amiodarone within 90 days prior to first dose.
14. Use of medications that increase serum levels of phosphorus and/or calcium.
15. Current use of therapeutic doses of warfarin sodium or any other coumadin-derivative anticoagulants. Heparin and/or low molecular weight heparins or other anticoagulants are allowed.
16. Insufficient bone marrow function
 - ANC $< 1,000/\text{mm}^3$ [$1.0 \times 10^9/\text{L}$]
 - Platelets $< 75,000/\text{mm}^3$ [$75 \times 10^9/\text{L}$]
 - Hemoglobin $< 10.0 \text{ g/dL}$
17. Insufficient hepatic and renal function
 - Total bilirubin $> 1.5 \times \text{ULN}$ (unless evidence of Gilbert's disease)
 - AST/SGOT and ALT/SGPT $> 2.5 \times \text{ULN}$
 - Serum creatinine $\geq \text{ULN}$ and/or calculated or measured creatinine clearance $< 75\% \text{ LLN}$
18. Calcium-phosphate homeostasis
 - Inorganic phosphorus outside of normal limits
 - Total and ionized serum calcium outside of normal limits
19. Clinically significant cardiac disease including any of the following:
 - Congestive heart failure requiring treatment (NYHA grade ≥ 2), LVEF $< 50\%$ as determined by MUGA scan or ECHO, or uncontrolled hypertension (refer to WHO-ISH guidelines)
 - History or presence of clinically significant ventricular arrhythmias, atrial fibrillation, resting bradycardia, or conduction abnormality
 - Unstable angina pectoris or acute myocardial infarction ≤ 3 months prior to starting study drug
 - QTcF $> 450 \text{ msec}$ (both genders)
 - History of congenital long QT syndrome
20. Pregnant or nursing (lactating) women, where pregnancy is defined as the state of a female after conception and until the termination of gestation, confirmed by a positive hCG laboratory test
21. Known positive serology for HIV, active Hepatitis B, and/or active Hepatitis C infection.
22. Study medication cannot be administered through G-tube, unless additional information from the manufacturer becomes available in the future.

23. Women of child-bearing potential, defined as all women physiologically capable of becoming pregnant, unless they are using highly effective methods of contraception during dosing and for 3 months following the discontinuation of study treatment must be used by both sexes (=female patients and their male partners). Highly effective contraception methods include:
- Total abstinence (when this is in line with the preferred and usual lifestyle of the subject. Periodic abstinence (e.g., calendar, ovulation, symptothermal, post-ovulation methods) and withdrawal are not acceptable methods of contraception)
 - Female sterilization (have had surgical bilateral oophorectomy with or without hysterectomy) or tubal ligation at least six weeks before taking study treatment. In case of oophorectomy alone, only when the reproductive status of the woman has been confirmed by follow up hormone level assessment
 - Male sterilization (at least 6 months prior to screening). For female subjects on the study the vasectomized male partner should be the sole partner for that subject.
 - Combination of the following (a+b or a+c, or b+c):
 - a. Use of oral, injected or implanted hormonal methods of contraception or other forms of hormonal contraception that have comparable efficacy (failure rate <1%), for example hormone vaginal ring or transdermal hormone contraception
 - b. Placement of an intrauterine device (IUD) or intrauterine system (IUS)
 - c. Barrier methods of contraception: Condom or Occlusive cap (diaphragm or cervical/vault caps) with spermicidal foam/gel/film/cream/vaginal suppository

Note: Oral contraceptives (OC), injected or implanted hormonal methods are not allowed as the sole method of contraception because BGJ398 (infigratinib) has not been characterized with respect to the potential to interfere with PK and/or the effectiveness of OCs.

Post-menopausal women are allowed to participate in this study. Women are considered post-menopausal and not of child bearing potential if they have had 12 months of natural (spontaneous) amenorrhea with an appropriate clinical profile (e.g. age appropriate, history of vasomotor symptoms) or have had surgical bilateral oophorectomy (with or without hysterectomy) or tubal ligation at least six weeks ago. In the case of oophorectomy alone, only when the reproductive status of the woman has been confirmed by follow up hormone level assessment is she considered not of child bearing potential.

24. Sexually active males unless they use a condom during intercourse while taking drug and for 3 months after the last dose of the study drug and should not father a child in this period. A condom is required to be used also by vasectomized men in order to prevent delivery of the drug via seminal fluid.

6 Treatment

The investigational drug will be BGJ398 (infigratinib) as an oral formulation.

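### Exclusion 8 is worded in reverse: in all four bullets, ongoing toxicity above Grade 2 lifts the 2-week exclusion, and inclusion 9 does not close the gap for wide-field external radiotherapy

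*Combined protocol and SAP*

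**What the plan says.** Section 5.2 opens with the rule "Patients eligible for this study must not meet any of the following criteria", so meeting any one item excludes the patient. Item 8 is introduced as "Treatment with any of the following anti-cancer therapies prior to the first dose of BGJ398 (infigratinib) within the stated timeframes". Its four bullets are:

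- chemotherapy: "Cyclical chemotherapy (intravenous) within a period of 2 weeks unless there are ongoing side effects" above Grade 2;
- biological therapy, including small molecules: "within a period of time that is ≤ 2 weeks prior to starting study drug unless there are ongoing side effects" above Grade 2;
- investigational agents: "Any other investigational agents within a period ≤ 2 weeks prior to starting study drug unless there are ongoing side effects" above Grade 2;
- radiotherapy: "Wide field radiotherapy (including radioisotopes) ≤ 2 weeks prior to starting study drug unless there are ongoing side effects" above Grade 2.

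Inclusion 9 in Section 5.1 is a separate recovery requirement: "Recovery from adverse events of previous systemic anti-cancer therapies to baseline or grade 1". It has two exceptions, alopecia and stable neuropathy of grade 2 or lower from earlier cancer treatment. It is limited to systemic therapies.

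Section 9.2 requires source documents for every criterion. It lets the PI clarify eligibility criteria but not overturn them.

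**The concern.** A washout rule normally protects a patient who has not yet recovered from earlier treatment. Here the exception clause works against that purpose, because unresolved toxicity of a higher grade removes the exclusion. The same construction appears in all four bullets, so it is not an isolated slip in one line, and no other part of the documents corrects it.

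Two things are at stake. The first is patient safety at entry. The second is the clarity of the safety data. Safety and tolerability are a secondary objective (Section 3.2), and patients count as evaluable for toxicity from their first treatment (Section 7.3.1), so unresolved effects of earlier treatment could be carried into the on-study record.

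**Working it through.** No figure in the plan bears on this point, so the check is one of logic.

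**Step 1: exclusion 8 alone.** Read literally, a patient is excluded if therapy was given within 2 weeks AND NOT (side effects above Grade 2 are ongoing).

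| Case | Time since therapy | Ongoing side effects | Excluded by item 8? |
|---|---|---|---|
| (a) | within 2 weeks | Grade 2 or lower, or none | Yes |
| (b) | within 2 weeks | above Grade 2 | No |
| (c) | more than 2 weeks | any grade | No |

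Cases (a) and (b) are the wrong way round: of two recently treated patients, the one with worse toxicity passes.

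**Step 2: case (b) crossed with inclusion 9.** Section 5.1 requires every inclusion criterion to be met, so passing exclusion 8 is not enough.

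| Earlier therapy | Does inclusion 9 apply? | Outcome in case (b) |
|---|---|---|
| Intravenous chemotherapy | Yes | Ineligible, unless the toxicity counts as baseline or falls under the alopecia exception; the neuropathy exception stops at grade 2 |
| Biological therapy or small molecules | Yes | Same |
| Systemic investigational agent | Yes | Same |
| Radioisotopes | Unclear: placed in the radiotherapy bullet, but could be read as systemic | Depends on the reading |
| External wide-field radiotherapy | No | Passes both criteria |

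**Step 3: other criteria that might stop the radiotherapy patient.** These are ECOG status of 1 or lower (inclusion 4), ability to swallow and retain oral medication (inclusion 8), gastrointestinal function (exclusion 6), marrow function (exclusion 16), hepatic and renal function (exclusion 17) and the bar on G-tube dosing (exclusion 22). Each catches particular toxicities. None is a general requirement to have recovered from radiotherapy.

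**Step 4: the grade thresholds.** Exclusion 8 turns on toxicity above Grade 2; inclusion 9 turns on baseline or grade 1. Where both apply, the stricter one decides, so the difference has little practical effect for systemic therapy. For radiotherapy only the reversed exclusion 8 threshold is available.

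**Step 5: case (c) after radiotherapy.** A patient irradiated more than 2 weeks earlier with ongoing side effects above Grade 2 also passes both criteria. This follows from the scope of inclusion 9 and not from the reversed clause, so correcting the clause does not by itself settle it.

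**The case against.** The strongest reply is that the practical gap is narrow. For three of the four bullets, inclusion 9 does nearly all the work that exclusion 8 fails to do. What remains is a patient with recent wide-field radiotherapy, ongoing toxicity from it above Grade 2, good performance status, intact swallowing and adequate organ function. The other criteria will remove many such patients. Eligibility is also checked centrally against source documents before treatment, where an evident drafting slip could be raised, and the five-level attribution scale in Section 10.2 helps to separate earlier toxicity from drug effects. The intended meaning was probably that 2 weeks is enough unless toxicity persists.

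Most of this stands, and it limits the size of the point. It does not remove it. The intended meaning is an inference and is not what is written. The PI may clarify a criterion but not overturn it, and sites at several centers must document eligibility against the text as it stands.

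A reader might go further and infer that the clause contaminates the primary endpoint, through tumor shrinkage from recent radiotherapy being counted as response. The documents do not support tying that to the reversed wording. Exclusion 8 places no limit on radiotherapy that is not wide-field, or on wide-field treatment more than 2 weeks earlier, so most of that possibility would remain after the clause was corrected. It is largely a separate question.

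**Conclusion.** The wording is wrong as written: in all four bullets the exception favors the recently treated patient with worse toxicity. That conclusion needs only the text of Section 5.2. The live consequence is mainly confined to external wide-field radiotherapy within 2 weeks of the first dose, because inclusion 9 still blocks nearly all the corresponding patients after systemic therapy. This rests on reading external radiotherapy as not systemic; the position of radioisotopes is open.

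The documents give no basis for a count of affected patients. It may be zero. It would be a mistake to infer that all four bullets are open safety gaps, or that a stated share of the 20-patient sample is affected. The sample size, the futility rule and the other Simon design figures do not change. The case for correction is that this is an operative eligibility rule with a safety purpose, its direction is plainly reversed, and the repair is nearly free.

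**What to change.** Reword the exception clause in all four bullets of exclusion 8 so that ongoing toxicity does not lift the exclusion. In the same amendment, reconcile exclusion 8 with inclusion 9 on two matters: the grade threshold each uses, and whether side effects of radiotherapy, including radioisotopes, come under the recovery requirement. The sponsor should choose the thresholds and decide the scope; no particular washout, grade or recovery rule is proposed here.

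The cost is amendment text and a matching change to the eligibility checklist. No statistical section needs to be altered.
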